For the purposes of determining a safety endpoint, the following conditions are not considered adverse incidents, have been known to occur with similar microneedling procedures, and are expected to occur as part of a normal and necessary healing process after each treatment:

- a) Erythema – superficial reddening of the skin in the area treated
- b) Edema – mild swelling in the area treated
- c) Crusting – a scab
- d) Mild to moderate pain during treatment that resolves within 2 hours after treatment
- e) Hypo/hyperpigmentation, the skin in the treatment area becomes temporarily lighter or darker than the surrounding skin but resolves with 90 days of treatment
- f) Mild Pruritis – mild itching around the treatment area
- g) Mild to moderate petechiae – pinpoint bleeding that resolves (stops) within 1 hour of treatment

For the purposes of determining a safety endpoint, the following six conditions have been known to occur with similar microneedling procedures and are considered adverse incidents regardless if they result in the need for medical intervention or not:

- 1) Moderate to severe pruritis– severe itching not resolving within 24 hours
- 2) Moderate to severe pain that continues more than 2 hours after the end of the treatment.
- 3) The presence of active infection in the treatment area after treatment

- 4) Fever developing after treatment
- 5) Hypo/hyperpigmentation, the skin in the treatment area becomes lighter or darker than the surrounding skin and does not resolve with 90 days of treatment
- 6) Moderate to severe petechiae – pinpoint bleeding that does not resolve within 1 hour of treatment

Safety endpoint analysis

Subjects will be photographed approximately 180 days after the last treatment and asked about the incidence and/or persistence of any of the above six listed conditions considered to be adverse incidents.

Patient Population

The patient cohort shall be comprised of not less than 35 qualified persons (using the inclusion criteria). Any more than 5 dropouts shall be replaced so that a total of at least 30 participants complete the trial.

Regulatory Compliance

The trial will be conducted in compliance with this protocol, GCP, and the applicable regulatory requirements of the United States.

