The trial shall be under the supervision of a duly accredited Institutional Review Board or equivalent ethics oversight committee. The SkinStylus® and this trial is considered a Non-Significant Risk (NSR) as the device is being used entirely within its foreign agency cleared performance specification.

The trial shall be monitored at planned and at unannounced intervals by a Registered Nurse who has appropriate training in the conduct of medical research. The RN Monitor shall ensure the trial is conducted according to the requirements of the approved protocol. In addition to examining the Case Report Forms (CRF) for each participant the RN Monitor shall review the digital photographs taken and will report to the PI any instance where an injury may have occurred.

The PI and all sub-PI's shall be appropriately trained in the *Protection of Human Subjects* as provided by the National Institute of Health or equivalent body.

C. Trial Design

1. The SkinStylus has been designated as a non-significant risk and therefore will be granted an Investigational Device Exemption (IDE). There are no meaningful

changes to the SkinStylus® instructions for use and specifically no new risks will be introduced.

2. There are three endpoints under investigation. The primary endpoint is a statistically significantly improvement using the VAS scale on page 7. The secondary endpoint is patient feedback by the Subject Satisfaction Survey on page 7. The third endpoint is safety related and is the absence of adverse incidents as previously defined.
3. The trial shall be blinded and bias minimized in that three (3) physicians who are either dermatologists or plastic surgeons (and not affiliated with the trial or Esthetic Education LLC) shall review the baseline and treatment photographs and score them using the VAS scale (see page 7).
4. Inclusion Criteria - patients age 23 years or older as described on page 6. The subjects shall all be volunteers. Subjects shall not be hand picked or otherwise manipulated or shown favor. There will be some effort expended to ensure reasonable representations of both sexes and of all Fitzpatrick Skin Types as shown below:

Type	Score	Description
I	0-6	Skin always burns; never tans. (Pale peach, blond, or red hair, blue eyes, freckles)
II	7-13	Skin usually burns, tans minimally (peach; fair; blond or red hair; blue, green, or hazel eyes)
III	14-20	Skin sometimes mild burn, tans uniformly (light brown; fair with any hair or eye color)

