IV	21-27	Skin burns minimally, always tans well (moderate brown)
V	28-34	Skin very rarely burns, tans very easily (dark brown)
VI	35-36	Skin never burns, always tans (deeply pigmented dark brown to darkest brown)

5. Exclusion Criteria – patients with any of the following shall be excluded from the study.
 - a. Women who are or think they may be pregnant

- b. Participants currently taking Coumadin/Warfarin® or heparin
- c. Any type of bleeding disorder
- d. Any history of keloid formation
- e. Lidocaine, tetracaine, prilocaine, bupivacaine, or benzocaine hypersensitivity
- f. Patients with mental disorders
- g. Patients with metal implants around the proposed treatment areas
- h. Patients with any undefined wasting disease (Cachexia for example)
- i. Presence of an active infection in the treatment area other than mild acne
- j. Presence of tumors or those who are being treated by chemotherapy or radiation therapy
- k. Presence of severe cardiovascular and cerebrovascular disease
- l. Presence of renal failure

6. Withdrawal from the study - the patient will be withdrawn from the study upon his/her request or if the PI determines the patient has become part of the excluded population. For example, during the trial a female participant discovers she has unexpectedly become pregnant.

7. The PI or his designee will discuss the study with each potential participant reviewing the SkinStylus® and its operation, the treatment protocol, the need of completion of the trial as written, the inclusion and exclusion criteria; the warnings and contraindications and the taking of photographs prior to obtaining informed consent. Any potential participant not meeting all the selection requirements shall not be accepted into the trial and therefore no informed consent from them shall be required.

8. Adverse Incidents – adverse incidents are defined above. The PI shall be immediately informed whenever an adverse incident, as defined above, is detected or even suspected to have occurred. The circumstances relating to adverse incidents, their resolution and the participant's condition and treatment shall be recorded on the CRF.

9. Photographs

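### The expected-reaction and adverse-incident lists leave some events on neither list, so the safety endpoint can understate harm

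*Combined protocol and SAP*

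**What the plan says.** The Safety Endpoint section of the combined protocol and SAP sets out two lists. Items a) to g) are expected reactions that are kept out of the endpoint. Items 1) to 6) are the adverse incidents.

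- Pain: item d) is "Mild to moderate pain during treatment that resolves within 2 hours after treatment"; item 2) is "Moderate to severe pain that continues more than 2 hours after the end of the treatment".
- Itching: item f) is "mild itching around the treatment area", with no time limit; item 1) is "Moderate to severe pruritis– severe itching not resolving within 24 hours".
- Swelling: item b) is "mild swelling in the area treated", with no matching incident.
- Redness: item a) is "superficial reddening of the skin in the area treated", with no time limit and no matching incident. Crusting, item c), is treated the same way.
- Petechiae: item g) is labelled mild to moderate and stops within 1 hour; item 6) is labelled moderate to severe and does not.
- Pigmentation: items e) and 5) divide at 90 days.

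No rule covers an event that is on neither list.

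The later safety steps refer back to these definitions. Section C, item 2 says: "The third endpoint is safety related and is the absence of adverse incidents as previously defined". Section D asks for a relative lack of the same incidents. Section C, item 8 says "The PI shall be immediately informed whenever an adverse incident, as defined above, is detected or even suspected to have occurred", and its CRF recording duty also concerns adverse incidents. At the 180-day safety visit, participants are asked about the six conditions only. Section C, item 11 makes the CRF the sole source record.

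**The concern.** When a safety endpoint is built from a list of what counts and a list of what does not, every relevant event should fall on exactly one of them. Here the lists set limits on both severity and duration, and the limits do not line up. An event can be too severe or too long-lasting to be expected and still fail to be an incident.

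The trial is meant to supply objective evidence of safe use, and the incident definition governs what is counted, notified and asked about. An event on neither list has no defined route into the safety result. Any resulting error lowers the count and cannot raise it.

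**Working it through.** The plan states no figure for the safety endpoint, so there is nothing to reproduce. The check places each combination of severity (mild, moderate, severe) and duration (within or beyond the stated limit) on the two lists. For itching and petechiae the time limit stands only in the description after the dash, while severity can be read from the label or from the description. Both readings are shown.

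| Condition | Expected | Incident | On neither list |
|---|---|---|---|
| Pain | d: mild or moderate, within 2 h | 2: moderate or severe, beyond 2 h | severe within 2 h; mild beyond 2 h |
| Itching, severity from label | f: mild, any duration | 1: moderate or severe, beyond 24 h | moderate within 24 h; severe within 24 h |
| Itching, severity from description | f: mild, any duration | 1: severe, beyond 24 h | the two above, plus moderate beyond 24 h |
| Petechiae, severity from label | g: mild or moderate, within 1 h | 6: moderate or severe, beyond 1 h | severe within 1 h; mild beyond 1 h |
| Petechiae, by description | g: any, within 1 h | 6: any, beyond 1 h | none |
| Edema | b: mild, any duration | none | moderate; severe |
| Pigmentation | e: resolved by 90 days | 5: not resolved by 90 days | none |
| Erythema, crusting | a, c: no time limit | none | none; always expected |

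Counts for pain, itching and petechiae:

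- Labels throughout: 2 + 2 + 2 = 6.
- Descriptions throughout: 2 + 3 + 0 = 5.
- Missed on both readings: 2 (pain) + 2 (itching) = 4.

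Moderate and severe edema come on top. The label of item b) carries no severity, so that gap rests on its description, but with no edema incident on the other list such cases go uncounted either way.

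**Illustration only.** The documents give no event rates. Assume a proportion p of 30 participants has a relevant event, and that for a share g of them the event is on neither list. The chance of counting no incident is (1 − p(1 − g))^30, against (1 − p)^30 if all were counted.

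| p | All counted | g = 25% | g = 50% | g = 75% |
|---|---|---|---|---|
| 10% | 4.2% | 9.6% | 21.5% | 46.8% |
| 20% | 0.1% | 0.8% | 4.2% | 21.5% |

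At p = 10% and g = 50%, the expected count falls from 30 × 0.10 = 3.0 to 30 × 0.05 = 1.5. For scale, 3 of 30 is 10% (Clopper-Pearson 95% interval 2.1% to 26.5%), while 0 of 30 is 0% with an upper limit of 11.6%.

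**The case against.** Setting expected procedural reactions apart in advance is legitimate, and whether brief itching or lingering mild pain should count is a clinical choice. That stands, and it is why the fix proposes no threshold. It does not explain why the plan is silent on these events.

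Several stronger readings are tempting, and the documents do not support them:

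- A reader might infer that lasting redness falls between the lists. It does not: erythema is expressly expected, without a time limit. That is a separate defect. The list's preamble ties expected reactions to normal healing, so it is arguable that very late redness leaves the list. Even then, none of the six incidents would catch it.
- A reader might infer that prolonged moderate itching is plainly excluded. Under item 1's label it is an incident; only the description leaves it out.
- A reader might infer that the lists fail to meet throughout. Pigmentation divides cleanly, and so do petechiae by their descriptions.
- A reader might infer that unlisted events are lost altogether. The nurse monitor reviews CRFs and photographs and reports possible injuries to the principal investigator (Regulatory Compliance), item C.8 is triggered by suspicion alone, and Section E includes post-treatment complications in the analysis. These are partial backstops. The complications are undefined, neither they nor the monitor's reports are tied to the endpoint, suspicion under C.8 must still be of a defined incident, and photographs do not show pain or itching. The general commitment to GCP does not alter the endpoint's definition.
- A reader might infer a known downward bias. No event rate is given, and Section D sets no threshold for a relative lack, so the illustration changes no stated decision.

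**Conclusion.** The point holds as a gap in definitions. Severe pain resolving within 2 hours, mild pain beyond 2 hours, moderate or severe itching resolving within 24 hours, and moderate or severe edema are on neither list. With severity read from the labels, so are severe petechiae within 1 hour and mild petechiae beyond it. Item 1 contradicts itself. Separately, persistent erythema and crusting can never count.

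Because the endpoint, notification, incident recording and the 180-day question all rest on the six conditions, the safety endpoint can understate harm. The direction follows from the text. The size does not, and the illustration depends wholly on assumed rates. The conclusion assumes that site staff apply the lists as written.

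**What to change.** Three wording changes before enrolment:

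1. In the Safety Endpoint section and in C.8, state that any event in the treated area, during or after treatment, that does not fully meet any one of items a) to g) is recorded in the CRF with its severity and duration. Report it alongside the safety endpoint, whether or not it is one of the six conditions.
2. Widen the 180-day question to any persisting event, naming redness and crusting. The first change alone would miss these, because they satisfy items a) and c) however long they last.
3. Have the sponsor reconcile the label of item 1 with its description, and the severity and time limits of the two lists with each other.

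Where those limits should lie is for the sponsor to settle; none is proposed here. The cost is protocol and CRF wording, slightly more recording, and possibly a higher reported event rate.

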- b. The technician administering the treatment shall further clean the treatment areas, if necessary.
- c. The hypertrophic scar to be treated shall be divided into two equal segments and the technician shall randomly choose one half to be treated.

- d. The technician shall describe in the CRF, which half of the scar was treated.
- e. Subsequent treatments shall only treat the same half of the scar that was initially designated the treatment side.
- f. If the scar is to be locally anesthetized, the entire scar (both halves) are to be anesthetized.
- g. A proprietary glide serum, EstheCeuticals® HA-Cu Serum, shall be applied prior to treatment and again as necessary. The purpose of the serum is to act as a glide and no therapeutic effect is known or anticipated. This serum has been used in several hundred microneedling treatments without any incidence of adverse events.
- h. The depth settings and clinical endpoints shall be established by the PI.
- i. Each participant shall receive three SkinStylus treatments .
- j. Each participant shall receive one treatment using each of the three different array configurations. The order in which each is used shall be randomized at intake but a different array configuration must be used in each of the three treatments.
- k. The treatments shall be not less than 12 days or more than 14 days apart.
- l. The treatments shall consist of 2 to 3 passes at the targeted area over a period of 15-30 minutes.
- m. While the technician may adjust the treatment settings, the treatment settings shall remain within the range specified by the PI, usually 2.5mm depth.
- n. At the conclusion of treatment the technician completes the CRF as stipulated.
- o. 90 days following the final treatment the post treatment photograph shall be taken and recorded in the CRF. There may be other photographs taken periodically during the trial in addition to the dermal spectroscope readings taken.
- p. 180 days following the initial treatment the patients shall be evaluated to provided objective evidence of what adverse incidents, as previously defined, may have occurred.

D. Determination of Results

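### Fever counts as an adverse incident with no onset window or attribution rule, so unrelated illness over about half a year enters the safety endpoint

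*Combined protocol and SAP*

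**What the plan says.** The Safety Endpoint section lists six conditions that "are considered adverse incidents regardless if they result in the need for medical intervention or not". Item 4 is "Fever developing after treatment", with nothing further: no temperature, onset window, duration or link to the device.

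The other five are narrower. Pruritus, pain, pigmentation change and petechiae each carry a limit on duration or resolution (24 hours, 2 hours, 90 days, 1 hour); for example, "Moderate to severe pain that continues more than 2 hours after the end of the treatment". Infection has no time limit but is confined to a site: "The presence of active infection in the treatment area after treatment".

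Under Safety endpoint analysis, subjects are "asked about the incidence and/or persistence of any of the above six listed conditions considered to be adverse incidents". That section places the question about 180 days after the last treatment. Section C item 12(p) instead says "180 days following the initial treatment the patients shall be evaluated".

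Section C item 8 requires the PI to be told at once of any detected or suspected incident, with its circumstances and resolution recorded on the CRF.

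The success criterion is worded in three ways. In Section C item 2 the third endpoint "is the absence of adverse incidents as previously defined". Section D asks for a relative lack of incidents and Section E for a relative absence. Neither of the last two gives a threshold or a comparator.

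**The concern.** A site that applies item 4 as written must record as an adverse incident any fever, from any cause, between the first session and the safety visit. Over about half a year that includes ordinary illness that has nothing to do with microneedling.

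The split-scar design does not help. Section C items 12(c) to (e) make the other half of the same scar the control, and a fever belongs to the person and not to one half. There is no untreated group from which a background fever rate could be estimated and subtracted.

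The consequence depends on which success wording governs. Under the absence wording, one unrelated fever is enough to fail the safety endpoint. Under the two relative wordings it is not, but with no threshold and no attribution rule, someone must decide which fevers matter once they are known. Either way the fever count does not separate device harm from background illness, although the trial's stated purpose is objective evidence of safe and effective use.

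**Working it through.** **Plan's own figure.** There is none to reproduce. The plan states no expected incident rate, threshold or power for safety. The 80% power with 30 subjects in Section E concerns the VAS comparison and does not bear on this point.

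**Inputs from the documents**
- Completers: at least 30 (Patient Population); at least 35 enrolled.
- Three sessions, 12 to 14 days apart (Section C items 12(i) and 12(k)), so 24 to 28 days from first to last.
- Safety question 180 days after the initial session: 180 days from the first session. If 180 days after the last: 180 + 24 = 204 to 180 + 28 = 208 days from the first. The range used is therefore 180 to 208 days.

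**Input that is an assumption.** The rate r of unrelated fever per person-year is not given. The main range is 0.05 to 0.1; values on either side are shown for sensitivity.

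**Formula.** With n participants followed for d days and a device that adds no fevers, the expected number is m = n × r × d / 365.25, and the chance of none is P(0) = exp(−m).

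**Results, n = 30**

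| Assumed r | m at 180 days | P(0) | m at 208 days | P(0) |
|---|---|---|---|---|
| 0.02 | 0.30 | 74% | 0.34 | 71% |
| 0.05 | 0.74 | 48% | 0.85 | 43% |
| 0.1 | 1.48 | 23% | 1.71 | 18% |
| 0.3 | 4.44 | 1.2% | 5.13 | 0.6% |

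Worked example: 30 × 0.1 × 180 / 365.25 = 1.48, and exp(−1.48) = 0.23.

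If all 35 enrolled were followed throughout, P(0) would be 37–42% at r = 0.05 and 14–18% at r = 0.1. The plan guarantees only 30 completers, so the table is the fairer basis.

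**Break-even.** Let p be the per-person risk over follow-up. P(0) = (1 − p)^30 falls below one half when p exceeds 1 − 0.5^(1/30) = 2.3%. As a rate, this is ln 2 / (30 × d / 365.25) = 0.047 per person-year at 180 days and 0.041 at 208 days.

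**Effect of a window (illustration only; no length is recommended).** Suppose only the 7 days after each of three sessions counted, 21 days in all. At r = 0.1, m = 30 × 0.1 × 21 / 365.25 = 0.17 and P(0) = 84%, against 18–23% without a window. At r = 0.05, P(0) = 92%, against 43–48%.

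**The case against.** Several counter-arguments have force.

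- **The absence wording is one of three.** Section D, which says how results are determined, asks for a relative lack, and Section E for a relative absence. A few unrelated fevers need not fail either. This stands: every P(0) above matters only if a single incident means failure. But neither wording has a threshold, so the definition still does not settle which fevers count.
- **Incidents are captured as they happen.** Section C item 8 requires immediate reporting and a record of circumstances, so the 180-day question is not the only route. This also stands, but the rule applies to incidents as already defined and excludes nothing. The CRF is not in the documents, so whether it already has a field for onset date cannot be known.
- **The list is introduced as conditions known to occur with similar procedures.** This favours reading item 4 as procedure-related fever. It explains why fever was listed but does not tell a site which fevers to count.
- **Late recall can miss fevers.** True. The error is therefore not only towards over-counting, and the calculation assumes that every fever is reported.

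A reader might also infer three stronger points that the documents do not support. One is that fever alone lacks an onset window: the limits on the other items concern duration or resolution, and no item states an onset window. Another is that infection shares the defect: item 3 is confined to the treatment area, and none of the figures here concern it. The third is that inconvenient fevers would be dismissed afterwards. The plan leaves room for this, but nothing in it shows that it is intended.

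**Conclusion.** The point holds for item 4. Its definition has no onset, site or attribution limit, its incidence is asked about roughly 180 days later, and the half-scar control cannot correct for a systemic event. Read literally, it lets unrelated illness into the safety count.

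The size is conditional. Under the Section C absence wording, with 30 completers and an assumed 0.05 to 0.1 unrelated fevers per person-year, a harmless device would show no fever with a chance of 43–48% at the lower rate and 18–23% at the higher. Zero is less likely than not once per-person risk over follow-up exceeds about 2.3%. That is a low bar, but the documents give no rate to show that it is passed. A flat statement that a harmless device is unlikely to meet the safety endpoint therefore goes further than the text allows: it needs both an assumed rate and the strictest of the three wordings. Under the other two, the harm is a count with no pre-stated rule for interpreting it.

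This should be corrected before enrolment. It affects the third endpoint, not the primary one.

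**What to change.** For item 4 only:

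1. State an onset window after each session, with the length set by the PI before enrolment.
2. When a fever is reported under Section C item 8, record on the CRF the onset date, the preceding session and needle array, and the PI's judgement of relatedness.
3. Count in-window fevers in the safety endpoint. List all later fevers separately, with relatedness, so that none is lost.

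Leave item 3 (infection) without a window. It is already limited to the treatment area, and a window would take late infections there out of the endpoint count.

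Two conflicts need reconciling at the same time: the 180-day anchor (last treatment under Safety endpoint analysis, initial treatment in Section C item 12(p)), and the three wordings of the safety criterion in Sections C, D and E. A fever window alone does not supply the missing threshold.

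The cost is about one sentence in the definition and up to three CRF fields, fewer if the CRF already holds some of them. The downside is that a device-related fever with late onset would appear in the separate listing and not in the endpoint count.

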SkinStylus Microneedling System

Protocol for Clinical Study

Treatment of Ventral Torso Hypertrophic Scars

Trial Sponsor:

Esthetic Education LLC
[name]
[name]
[name]

Principle Investigator:

[name], MD

Trial number – 2017-002

04 August 2017

[figure not shown]
Protocol Synopsis for EE 2017-02

Title of Study:	The Clinical Efficacy And Safety Of SkinStylus Microneedling System for Ventral Torso Hypertrophic Scars: Clinical Results With 30 Patients
Principal Investigator:	[name], M.D. F.A.A.D
Study Design:	Blinded, bias minimized comparison of pre and post treatment photographs
Target Population:	General population over the age of 22
Duration of Study:	Approximately 6 months
Treatment	SkinStylus® Microneedling
Study Objective:	This is a study to evaluate the efficacy of SkinStylus Microneedling for ventral torso hypertrophic scars

PROTOCOL APPROVAL PAGE

We the undersigned have reviewed this protocol and agree that it contains all relevant information and appropriate safeguards for human participants as required by the UK MHRA, GCP, ICH and USFDA requirements.

[figure not shown]
We further agree that the protocol will be executed exactly as written and approved by the Institutional Review Board (IRB) and/or Ethics Committee. Any change required or proposed shall be reviewed by the IRB/Ethics Committee prior to its implementation.

[figure not shown]
[name]
Owner
Esthetics Education, Inc.

8/21/17

Date

PT

[name], MD

8/8/2017

Date

Investigator Signature Sheet

I have read the attached protocol and agree that it contains all the necessary details for performing the study.

I will provide copies of this protocol and of the preclinical information on the investigational product, which was furnished to me by the sponsor, to all members of the study team responsible to me who participate in the study. I will discuss this material with them to assure that they are fully informed regarding the study device and the conduct of the study.

Once this protocol has been approved by the Institutional Review Board (IRB), I will not modify it without obtaining the prior approval of the sponsor and of the IRB. I will submit the protocol modifications and/or any informed consent form modifications to the sponsor and the IRB, and approval will be obtained before any modifications are implemented.

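### Apart from unsolicited reporting, patients are asked about the six adverse incidents only at about 180 days, from two conflicting start dates, and no safety denominator is stated

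*Combined protocol and SAP*

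**What the plan says.** The Safety Endpoint section lists six adverse incidents. Three carry short limits: itching (24 hours), pain (2 hours) and petechiae (1 hour). Persistent pigment change has a 90-day limit. Infection and fever have none.

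Safety endpoint analysis then sets the questioning: "Subjects will be photographed approximately 180 days after the last treatment", when they are to be "asked about the incidence and/or persistence of any of the above six listed conditions considered to be adverse incidents". C.12.p dates the evaluation for the same incidents differently: "180 days following the initial treatment the patients shall be evaluated". C.12.i gives three treatments, and C.12.k spaces them: "The treatments shall be not less than 12 days or more than 14 days apart". The Protocol Synopsis gives the study duration as "Approximately 6 months".

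Three other provisions can bring an incident onto the record earlier:

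- C.8: "The PI shall be immediately informed whenever an adverse incident, as defined above, is detected or even suspected to have occurred". The circumstances and outcome then go on the CRF.
- C.12.n: "At the conclusion of treatment the technician completes the CRF as stipulated".
- Regulatory Compliance: the RN Monitor examines the CRFs and photographs and "will report to the PI any instance where an injury may have occurred".

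C.2, D and E judge the safety endpoint by the absence, or relative absence, of the incidents already defined. E also brings complications after treatment into the analysis without defining them. Patient Population requires at least 35 enrolled, with replacement only beyond five dropouts, so that no fewer than 30 finish. E describes a sample of 30 with assessable data. No section says over whom safety is counted.

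**The concern.** The stated purpose includes objective evidence of safe use, and the endpoint is met by few or no incidents. For an endpoint of that kind, an event that is not collected counts towards success. Whether pain lasted beyond 2 hours, or bleeding beyond 1 hour, is what separates an incident from an expected effect in the plan's own lists. A patient first asked months later must place the symptom on one side of that line from memory, and an examination at that point cannot see it.

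Three further gaps bear on the same endpoint. The visit has two dates. Complications outside the six incidents enter the analysis with no stated question to patients and no stated relation to the endpoint. And without a denominator, patients who leave after treatment may or may not be in the reported rate.

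**Working it through.** **The plan's own figure.** 35 enrolled − 5 unreplaced dropouts = 30 completers, which agrees with Patient Population and with the sample in E.

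**What the earlier routes can show.** C.8 governs what follows once an incident is detected or suspected; it schedules no detection. The CRF in C.12.n is completed when treatment ends, before limits of 1, 2 or 24 hours after treatment have run out, so that entry cannot show whether the same session's symptom outlasted its limit. The RN Monitor reviews CRFs and photographs, and photographs do not show itch, pain or fever. C.11.c makes the CRF the only source record. None of these schedules a question to the patient after the short limits have passed.

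**Calendar.** Take the first treatment as day 0 and the spacing as 12–14 days (C.12.k). The second treatment falls on days 12–14 and the third on days 2 × 12 = 24 to 2 × 14 = 28.

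- Counted from the last treatment, the visit is on days 24 + 180 = 204 to 28 + 180 = 208.
- Counted from the initial treatment, it is on day 180, which is 180 − 28 = 152 to 180 − 24 = 156 days after the last treatment.
- The two dates differ by 204 − 180 = 24 to 208 − 180 = 28 days.

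Recall, in days from treatment to questioning:

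| Treatment | Visit dated from last treatment | Visit dated from initial treatment | If also asked at existing contacts |
|---|---|---|---|
| 1 | 204–208 | 180 | 12–14 (at treatment 2) |
| 2 | 192–194 | 166–168 | 12–14 (at treatment 3) |
| 3 | 180 | 152–156 | 90 (at the photograph) |

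The full range under the present text is 152–208 days.

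**Does the synopsis settle the date?** At 30.44 days per month, 180 days is 5.9 months, and 204–208 days is 6.7–6.8 months. An approximate duration of 6 months, not stated to be per patient, cannot decide between them.

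**Denominator.** With no incidents, the upper limit of the exact two-sided 95% interval is 1 − 0.025^(1/n):

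- n = 30: 1 − 0.025^(1/30) = 11.6%
- n = 35: 1 − 0.025^(1/35) = 10.0%

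If five leavers had been treated and their status were unknown, the observed proportion could lie anywhere from 0/35 to 5/35 = 14.3%. That is an arithmetical bound, not an estimate.

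**The case against.** A reader might infer that nothing is captured before day 180. The documents do not support that. C.8 requires immediate notification and CRF recording, and monitoring takes place at planned and unannounced times. The endpoint is defined by the incidents themselves, not by answers at the final visit, so an incident recorded earlier would count. The CRF form and the consent text are not available here; either could hold a symptom prompt or reporting instructions. All of this stands. What remains is that the visible text schedules no earlier question to patients.

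A reader might also infer that complications outside the six incidents have no route to the record. That is too strong: the RN Monitor's duty to report possible injury is not confined to the six. The gap is a question to patients and a link to the endpoint.

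The date conflict does little to the recall problem. Both dates lie well beyond the 90-day pigment limit, and neither helps with an event measured in hours. It is a separate inconsistency, with no evident direction of bias.

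The 14.3% bound needs every leaver to have had an incident and none to have been recorded, despite C.8. An interval around it would be false precision. Nor does the text say that safety is restricted to completers: the sample of 30 in E sits next to the efficacy assessment. The plain contrast between 30 and 35 moves the zero-event limit by only 1.6 percentage points (11.6 − 10.0).

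**Conclusion.** The point holds in limited form and should be corrected. Outside unsolicited reporting, the only scheduled question to patients about the six incidents comes at about 180 days. Three of the six turn on 24-, 2- and 1-hour limits, so one that was not volunteered or noticed earlier depends on recall of 152–208 days. The two statements of the visit date are 24–28 days apart and must be reconciled; this review does not say which is right. If two separate visits are meant, the text should say so, and both would still fall at least 152 days after the last treatment. The added complications are neither asked about nor tied to the endpoint, and the safety denominator is unstated.

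It would go too far to conclude that incidents will be undercounted. The documents establish neither that an undercount would occur nor its size. The day counts assume the 12–14-day spacing is kept. The denominator figures assume exactly 35 patients, all treated at least once; 35 is the stated minimum, and replacements could raise it.

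**What to change.** - **Ask earlier.** Put a six-item checklist and an open question on any other event to each patient before treatments 2 and 3, at the 90-day photograph and at the final evaluation, and record the answers on the CRF. The hour-level limits would still be recalled rather than observed, but over 12–14 days for treatments 1 and 2 and 90 days for treatment 3. A short call soon after treatment 3 would shorten the last figure; it is an optional extra of about 35 calls.
- **Reconcile the date.** Give Safety endpoint analysis and C.12.p one start date.
- **Tie in the complications.** Report events from the open question as the complications named in E, beside the six-incident endpoint.
- **State the denominator.** Count every patient treated at least once, including withdrawn and replaced patients. State how many have unknown status, and give the per-patient incidence with an exact two-sided 95% interval.

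The cost is a slightly longer CRF, some protocol wording, and a reported incident rate that may rise. No new visit is needed, and neither the treatments nor the efficacy analysis changes.
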